3.3 Vulnerable patient populations

Pregnant women are considered a vulnerable population. As the condition of interest is a pregnancy-related and specific condition, it is unavoidable to exclude pregnant women from this research study. However, all risks to this vulnerable population will be minimized as most of the study will occur in the postpartum period. None of the study medications will be given until the patient has been postpartum for at least 6 hours.

Furthermore, neonates are considered a vulnerable population. We will be collecting data on neonatal rates on NICU admission or readmission to the hospital within 6 weeks postpartum to determine if there are any adverse effects of furosemide to the neonates. All risks to this vulnerable population will be less than minimal risk as furosemide has been used in lactating mothers previously with no neonatal adverse events noted at HUP. Also, no data currently exists in the literature to suggest that furosemide would pose any risk to breastfed infants.

3.4 Ensuring Necessary Medical Interventions

Being enrolled in this study will not change patients' clinical care in regards to antepartum course or delivery decisions. Their intrapartum management will not be different in any way. Regardless of randomization, the management will not be different in either arm apart from whether the intervention medication is given or not. Any elevations of blood pressure postpartum to greater or equal to 150/100 mmHg will receive amlodipine as first-line as an antihypertensive. Patients will be provided with prophylaxis against seizures and deep vein thrombosis appropriately as dictated by clinical care.

3.5 Potential Benefit to Participants

The potential benefit will be prevention of elevation of blood pressures to levels that are associated with high maternal among individuals randomized to the intervention arm. This will lead to a possible increased reduction in hypertension related morbidity, improved patient outcomes, and possibly decreased need for readmission or emergency room visits as compared to placebo. All efforts will be taken to minimize the risks associated with this study and the risks overall are considered minimal; therefore, the risk to subjects is reasonable compared to the benefit to patients and to society in general.

4 TREATMENT PLAN

4.1 Treatment Dosage and Administration

- 4.1.1 Oral furosemide 20 mg/day OR placebo for a total of 5 consecutive doses.
 - Missed or vomited doses will be noted and attempts made to provide them immediately when recognized for missed doses when inpatient. After discharge, patients will be instructed to take a dose as soon as possible if they have missed one. Furthermore, in the unlikely event that patients are discharged without a supply of their medications, we will ensure that the medication will be shipped to their house within 24 hours.

4.2 Toxicities and Dosing Delays/Dose Modifications

Any patient who receives treatment will be evaluable for toxicity. Each patient will be assessed for the development of toxicity according to development of ototoxicity or symptomatic derangements in electrolytes as determined by symptoms and corresponding daily basic metabolic profiles. In the event of the development of either, the medication will be discontinued.

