3.2 Exclusion Criteria

- **3.2.1** History of allergic reaction to furosemide
- 3.2.2 High risk comorbidities for which treatment may be indicated or contraindicated: class C or higher diabetes mellitus, chronic kidney disease or baseline creatinine >1.2, cardiac disorders including cardiomyopathy, congenital heart disease, angina or coronary heart disease, rheumatic disease (lupus), sickle cell disease
- 3.2.3 Baseline labs with K <3
- 3.2.4 Use of furosemide or other diuretics antepartum or intrapartum
- **3.2.5** Use of ototoxic agents including aminoglycosides (ie, Gentamicin for >1 dose), cephalosporins (ie Ancef >1 dose),
- **3.2.6** Patient unstable for protocol per investigator's judgement

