4.4 Duration of Therapy

Therapy with furosemide will continue daily for 5 days unless there is the development of intercurrent illness that prevents further administration of treatment, unacceptable adverse events, patient withdrawal from the study, or general or specific changes in the patient's condition render continued treatment unacceptable.

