4.6 Removal of Patients from Protocol Therapy

Patients will be removed from therapy when any of the criteria listed in Section 4.2 and 5.5 apply. The Principal Investigator will be notified and document the reason for study removal and the date the patient was removed in the Case Report Form. The patient will be followed-up per protocol.

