5.6 Removal of Subjects from Study

Patients can be taken off the study at any time at their own request, or they may be withdrawn at the discretion of the investigator for safety, behavioral or administrative reasons. The reason(s) for discontinuation will be documented and may include:

- 5.4.1 Patient voluntarily withdraws from treatment (follow-up permitted);
- 5.4.2 Patient withdraws consent (termination of treatment and follow-up);
- 5.4.3 Patient is unable to comply with protocol requirements;
- 5.4.4 Patient experiences toxicity that makes continuation in the protocol unsafe;
- 5.4.5 Treating physician judges continuation on the study would not be in the patient's best interest;
- 5.4.6 Lost to follow-up.

If a research subject cannot be located to document outcomes after a period of 2 weeks, the subject may be considered "lost to follow-up." All attempts to contact the subject during the first 2 weeks after discharge will be documented and will not exceed more than 2 phone texting messages and 1 phone call with or without voicemails.

5.4.6 The study is stopped.

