9 STUDY DESIGN/STUDY ENDPOINTS

This will be a prospective, randomized, double-blinded, single center study of the impact of a short course of furosemide on postpartum blood pressure recovery in women with hypertensive disorders of pregnancy (HDP). Please refer to Section 2.4 for end points.

Regarding stopping rules for safety or efficacy, we do not anticipate early termination of the study for either. Issues that would be of concern would be persistent hypokalemia (< 3.0) with therapy, ineffectiveness of therapy (as defined by the use of the same dosing of other antihypertensive agents for blood pressure control), and unexpected events (admission to ICU). Other findings that could trigger a safety review include the number of SAEs overall, the number of occurrences of a particular type of SAE, severe AEs, or increased frequency of events.

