9.2 Data Analyses Plans

To account for the multiple measurements per patient, we will employ repeated measure regression techniques. Measures of relative risk will include 95% confidence intervals. Descriptive statistics will be presented as mean with standard deviation, median with interquartile range, or proportion with 95% confidence interval based on data type and distribution. Comparisons between groups will be performed using a Chi-square or Fisher's exact test for categorical variables and parametric or non-parametric tests for continuous variables, as appropriate. Bivariable analysis will be used to determine variables (risk factors) that are independently associated with PPHTN. Intention-to-treat analyses will be conducted such that all patients with available follow-up measures will be included in the analysis. Blood-pressure measurements after randomization will be compared between groups with the use of a mixed-effects logistic-regression model, which will account for participants having different numbers of observations over a varying time span. Statistical analyses were conducted in SAS, version 9.4 (SAS Institute, Cary, NC). Two-tailed P values of <0.05 will be considered statistically significant.

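### Section 4.2 stops study drug for electrolyte changes only when they cause symptoms, so a measured on-treatment potassium below 3.0 without symptoms has no required dosing action

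*Combined protocol and SAP*

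**What the plan says.** All references are to the combined protocol and SAP.

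- **Mandatory stop (4.2).** Study drug must be discontinued for ototoxicity or for "symptomatic derangements in electrolytes as determined by symptoms and corresponding daily basic metabolic profiles". No potassium value is given. The section title mentions dosing delays and modifications, but the text has no rule to hold, recheck or resume.
- **Entry (3.2.3).** "Baseline labs with K <3" is an exclusion, with no symptom condition.
- **Trial level (section 9).** "persistent hypokalemia (< 3.0) with therapy" is listed as an issue of concern, in the paragraph on early termination and safety review.
- **Other routes off drug.** Section 4.4 continues therapy for 5 days unless there are, among other grounds, "unacceptable adverse events, patient withdrawal from the study", or a change in her condition that makes further treatment unacceptable. Section 5.6 lists "Patient experiences toxicity that makes continuation in the protocol unsafe" and, as a separate ground, the treating physician's view of her best interest.
- **Missed doses (4.1).** "Missed or vomited doses will be noted and attempts made to provide them immediately when recognized", for inpatients.
- **After removal.** "The patient will be followed-up per protocol" (4.6), and under intention to treat "all patients with available follow-up measures will be included in the analysis" (9.2).

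**The concern.** The sponsor draws a potassium line at 3.0 twice, once for starting treatment and once for the trial as a whole. The one rule that compels action for an individual woman on treatment does not use it and asks for symptoms instead. A woman at 2.9 before dose 1 may not start. A woman at 2.9 after dose 1, feeling well, has no dosing instruction, and the default in 4.4 is to continue.

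The people deciding are blinded (4.7), so they do not know whether the next capsule is a loop diuretic or lactose. Two women with the same result can be handled differently. What is at stake is the safety of the individual woman and consistent dosing, not the validity of the primary comparison.

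**Working it through.** **1. Which provisions respond to a measured potassium below 3.0 without symptoms?**

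| Section | Needs symptoms? | Potassium value? | Dosing action for the individual |
|---|---|---|---|
| 3.2.3 | No | Below 3 | Not enrolled (entry only) |
| 4.2 | Yes | None | Mandatory stop |
| 4.4 | No | None | Stop by judgement |
| 5.6 | No | None | Stop by judgement |
| 7.1, 7.2.1 | No | None | None: an abnormal value can be an adverse event and is then monitored |
| 5.7 | No | None | None: DSMB rule on a composite, trial level |
| 9 | No | Below 3.0, persistent | None: trial level |

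No row combines a potassium value with an action for a woman already on treatment.

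**2. How much dosing is left to judgement?** Inputs: 5 doses of 20 mg, 100 mg in all (4.1). If the value is found after dose k, the doses left are 5 − k and the amount left is (5 − k) × 20 mg.

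| Found after dose | Doses left | mg left of 100 |
|---|---|---|
| 1 | 4 | 80 |
| 2 | 3 | 60 |
| 3 | 2 | 40 |
| 4 | 1 | 20 |

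**3. Could a holding rule disturb the primary result?** Inputs from 9.1: 175 patients, 385 recruited, about 10% losses, a 45.6% rate and a 40% reduction.

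- Reading 175 as per group: 385 / 1.1 = 350 = 2 × 175, which fits the plan's total.
- Largest change in an arm's rate from one woman's outcome: 1/175 = 0.57 percentage points.
- Planned difference, reading 40% as relative: 45.6% × 0.6 = 27.4%, and 45.6 − 27.4 = 18.2 points.
- To move one arm by the whole planned difference, about 18.2 / 0.57 = 32 of its 175 women would each have to change outcome, all in the same direction, because of held doses.

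The protocol gives no frequency for potassium below 3.0, so no count of affected women can be calculated.

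**The case against.** The strongest reply is that clinicians can already stop. The best-interest ground in 5.6 and the change-in-condition ground in 4.4 are broad and need no symptoms, and usual clinical care continues throughout (5.3). That stands. A reader might infer that the protocol obliges a woman with a low potassium to keep taking capsules. It does not: what is missing is an automatic threshold, not a way to stop.

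A reader might also infer that the protocol contradicts itself. That goes too far. Deciding whether to start a diuretic differs from deciding whether to continue one in a woman under care, where replacement and rechecking are possible. Section 9 is trial level and speaks of persistent low values. The mismatch is a reason to state an individual rule, but it is not a contradiction.

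Nor does 4.1 tell staff to make up a deliberately withheld dose, which is not naturally a missed or vomited one. It would help only to say so.

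Finally, other safety material is not in the document supplied: the DSMB attachment cited in 10.4.1, the list of mandatory events promised in 5.7, and the section 11.2 to which 7.5 points. Any of these might mention hypokalemia. That limits confidence, but a dosing rule still belongs in 4.2.

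**Conclusion.** The point holds as a modest participant-safety and consistency gap. On the supplied text, a measured potassium below 3.0 without symptoms triggers no required dosing action, and 1 to 4 doses are left to judgement.

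It has no material effect on the primary result. That conclusion assumes that few women are affected, 175 per group, and a relative 40% reduction.

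A reader might conclude that any single value below 3.0 should end the course for good. The documents do not support that: section 9 is concerned with persistent values, and a transient low value can be corrected. Hold, replace and recheck, with discontinuation only if the value stays low, is the proportionate rule.

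**What to change.** Add to 4.2, for both arms:

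> For any measured on-treatment potassium <3.0, with or without symptoms, study drug is held, and potassium is replaced and rechecked per clinical care. Study drug may resume once potassium is at least 3.0 and is discontinued if it remains <3.0 on recheck. Held doses are recorded and not made up under 4.1. The woman stays in follow-up and in the intention-to-treat analysis.

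Under 2.3.2.6, report by arm the number of women with an on-treatment potassium measured and the number below 3.0. Label both descriptive, because 5.3 leaves testing to clinical staff and the women tested may be a selected group.

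The cost is one paragraph and two counts. The rule requires no scheduled test beyond the recheck in clinical care, and no change in sample size. Follow-up after removal (4.6) and inclusion in the analysis (9.2) are already planned.

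There are two downsides. A few women will miss some doses, at most 4 each when the value is found after dose 1. And the rule acts only on values that are measured: 4.2 assumes daily metabolic profiles while 5.3 makes testing discretionary, and this change does not settle that conflict.

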4.3 Concomitant Medications/Treatments

To maintain adequate blood pressure control postpartum (goal SBP < 150 mmHg and DBP < 100 mmHg) additional antihypertensive medications may be necessary, and should be used at any time in the postpartum period regardless of enrollment time and first study drug administration:

- 1) Any patient with persistent postpartum blood pressures, ≥150 mmHg systolic and/or ≥100 mmHg diastolic, will be started on 5 mg of amlodipine PO regardless of study arm or whether they are already taking another antihypertensive maintained from their antepartum period.
- 2) Any patient with persistent postpartum blood pressures, ≥160 mmHg systolic and/or 100 mmHg diastolic, will be started on 10 mg of amlodipine PO.
- 3) If blood pressures are still higher than the stated goal above, providers should utilize additional non-diuretic antihypertensive* medications known to be effective in managing elevated peripartum blood pressures.

*Providers will be asked to use non-diuretic medications first, however, if deemed medically necessary, furosemide will be allowed any time in the postpartum period. All uses of diuretic use for medically necessary reasons after enrollment of patient into the trial will be noted.

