Patients in both groups will undergo similar postpartum surveillance, including blood pressure and pulse assessment every 4 hours and urinary output measurements while hospitalized. Proper treatment for elevated blood pressures will be initiated immediately as soon as the elevated blood pressures are recognized, and will not be delayed for any study purposes including study drug administration. For this study, antihypertensive therapy will be initiated for persistently elevated postpartum blood pressures (BP) of ≥ 150 systolic or >100 mg Hg diastolic with 5 mg of amlodipine PO. Persistent severe range blood pressures (BP >160 mm Hg systolic or >110 mm Hg diastolic) will be treated with IV antihypertensives if needed, as well as 10 mg of amlodipine PO. If further antihypertensive medications are needed to maintain blood pressures <150/100, these will be per the discretion of the clinical staff in both arms. All physicians and clinical staff in Labor and Delivery as well the postpartum unit will be educated extensively to avoid diuretic antihypertensive medications unless deemed medically necessary. Furthermore, diagnostic and laboratory tests will be per the discretion of the clinical staff in both arms as well. Routinely, all patients undergoing cesarean section remain hospitalized for at least 3 days and all patients with preeclampsia with severe features are kept in the hospital for 3 days (per the recommendations of the ACOG Task Force on Hypertension in Pregnancy). 10 All patients will be followed at for 10 days after discharge as detailed below. Being enrolled in the study will not change the patient's clinical care at any time. Physicians, staff, and patients will be blinded to the intervention administered, unless a break in blinding is required for medical intervention of adverse effects.

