10.5 Adherence to the Protocol

Except for an emergency situation in which proper care for the protection, safety, and well-being of the study patient requires alternative treatment, the study shall be conducted exactly as described in the approved protocol.

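### Section 4.3 item 2 starts amlodipine 10 mg at diastolic 100, the same number as the 5 mg step, whereas section 5.3 places 10 mg at severe range (above 160 or above 110)

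*Combined protocol and SAP*

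**What the plan says.** Section 4.3 lists the amlodipine steps for persistent postpartum hypertension. Item 1 sets the lower step: "≥150 mmHg systolic and/or ≥100 mmHg diastolic, will be started on 5 mg of amlodipine PO regardless of study arm". Item 2 sets the higher step: "Any patient with persistent postpartum blood pressures, ≥160 mmHg systolic and/or 100 mmHg diastolic, will be started on 10 mg of amlodipine PO". No comparison sign is printed before the diastolic 100 in item 2. The section says these treatments "should be used at any time in the postpartum period regardless of enrollment time and first study drug administration".

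Section 5.3 gives the rule again. The lower step is for "persistently elevated postpartum blood pressures (BP) of ≥ 150 systolic or >100 mg Hg diastolic with 5 mg of amlodipine PO". For the higher step it says: "Persistent severe range blood pressures (BP >160 mm Hg systolic or >110 mm Hg diastolic) will be treated with IV antihypertensives if needed", and the same sentence adds the 10 mg dose: "treated with IV antihypertensives if needed, as well as 10 mg of amlodipine PO".

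Three other places bear on the cut-offs:
- Section 2.3.2.2 defines severe hypertension as above 160 systolic or above 110 diastolic.
- Section 3.1.1 uses 160/110 or higher for severe features.
- Section 3.4 makes amlodipine first line from 150/100 upward, without a dose.

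No section says whether 4.3 or 5.3 governs. Section 10.5 requires, outside emergencies, that "the study shall be conducted exactly as described in the approved protocol".

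**The concern.** A stepped rule needs a different threshold for each step. In 4.3 the systolic thresholds differ (150 and 160), but the diastolic number is 100 in both items. On diastolic pressure, then, the 5 mg step has no range of its own if item 2 means 100 or higher. Section 5.3 does separate the steps, at 100 and 110.

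Patient care is what is at stake. For a woman with a persistent 155/105, staff working from 4.3 item 2 would start 10 mg and staff working from 5.3 would start 5 mg. Both are operative dosing instructions, and whichever dose is given departs from one section. The higher dose would go to women below the protocol's own severe range, some of whom are also taking a blinded diuretic.

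**Working it through.** No sample-size or power figure is involved. The check applies each rule to the same persistent reading and compares the highest starting dose triggered.

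**Inputs**
- 4.3 item 1: 5 mg if SBP ≥150 and/or DBP ≥100.
- 4.3 item 2: 10 mg if SBP ≥160 and/or DBP 100. The missing sign is read as ≥, because 10 mg at exactly 100 but 5 mg at 101-109 would make no clinical sense.
- 5.3, lower step: 5 mg if SBP ≥150 or DBP >100.
- 5.3, higher step: 10 mg if SBP >160 or DBP >110.

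**As printed**

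| SBP | DBP | Section 4.3 | Section 5.3 |
|---|---|---|---|
| 145 | 98-99 | none | none |
| 145 | 100 | 10 mg | not triggered |
| 145 | 101-110 | 10 mg | 5 mg |
| 145 | 111 or more | 10 mg | 10 mg |
| 155 | 98-99 | 5 mg | 5 mg |
| 155 | 100-110 | 10 mg | 5 mg |
| 155 | 111 or more | 10 mg | 10 mg |
| 160 | 110 or less | 10 mg | 5 mg |

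With SBP below 160, the two sections differ by 10/5 = 2-fold at each of the 110 − 101 + 1 = 10 whole diastolic values from 101 to 110. At SBP 150-159 they also differ at DBP 100. Under 4.3 the 5 mg step stands alone only for SBP 150-159 with DBP below 100.

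**With item 2 changed to ≥110 and nothing else**

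| SBP | DBP | Section 4.3 | Section 5.3 |
|---|---|---|---|
| 145 | 100 | 5 mg | not triggered |
| 145 | 101-109 | 5 mg | 5 mg |
| 145 | 110 | 10 mg | 5 mg |
| 155 | 100-109 | 5 mg | 5 mg |
| 155 | 110 | 10 mg | 5 mg |
| 160 | 110 or less | 10 mg | 5 mg |

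This one change settles 9 of the 10 values (101-109). It also settles DBP 100 when SBP is 150-159. What remains comes from ≥ in one section against > in the other: DBP exactly 100 with SBP below 150, DBP exactly 110, and SBP exactly 160.

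**With the signs aligned as well** (5 mg at ≥150 and/or ≥100; 10 mg at ≥160 and/or ≥110), the two sections give the same dose at every reading.

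**Does the slip change who is treated?** Under 4.3, item 1 already starts amlodipine at every DBP of 100 or more. Item 2 adds only readings that already meet item 1, so the slip alters the starting dose and not the number of women started on an agent.

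**The case against.** The best reply is that this is an obvious typing error. Three other places put the severe diastolic cut-off at 110, so experienced staff would read through it. The missing sign may also be a fault of file conversion. Much of this stands: the intended value is hardly in doubt, and nobody appears to have chosen 100. But restoring a lost sign leaves the number in conflict with 5.3, and a prescribed starting dose should not depend on staff inferring the right figure. Nor does clinical discretion resolve it. Section 5.3 says "If further antihypertensive medications are needed to maintain blood pressures <150/100, these will be per the discretion of the clinical staff in both arms", which concerns further agents and not the starting dose of amlodipine.

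It is also fair to say that 5.3 never states that 10 mg is reserved for severe range. That reading is inferred from its two-step layout, though no other reading gives its 5 mg step a purpose.

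A reader might go further and infer any of the following. The documents do not support them.
- *Bias between arms, or a changed count of primary events.* The rule is the same in both blinded arms. Either dose is an added agent, and no section says how many women have pressures in the disputed range. At DBP exactly 100 with SBP below 150 the sections do differ on whether an agent is prescribed. That comes from the ≥ and > signs at a single value, and 100 is above the treatment goal in both sections.
- *Distortion of secondary outcomes, or effects of doses given before randomization.* The documents give no size or direction for either. A dose given before randomization cannot depend on the assigned arm, and allowing rescue at any time is a sound safety provision.
- *A need to redefine severe hypertension in 2.3.2.2.* That endpoint already uses the same cut-offs as 5.3, and rescue dosing can be corrected without touching it.

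**Conclusion.** The point holds as an error in an operative dosing threshold and should be fixed. Section 4.3 item 2 as printed conflicts with the step above it and with section 5.3. For SBP below 160 it doubles the starting dose relative to 5.3 at DBP 101-110, and at DBP 100 when SBP is 150-159.

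This rests on two assumptions: that item 2 means 100 or higher, and that the layout of 5.3 assigns 5 mg below severe range. It also takes the 100 in item 2 as the protocol's true text. If the approved protocol in fact prints 110 with a ≥ sign, only the boundary differences remain. The consequence is confined to rescue dosing and patient safety.

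**What to change.** Change section 4.3 item 2 to ≥160 mmHg systolic and/or ≥110 mmHg diastolic for amlodipine 10 mg.

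In the same clarification, use one set of signs for the rescue rules in both sections: 5 mg at ≥150 and/or ≥100, and 10 mg at ≥160 and/or ≥110. Item 1 of 4.3 and section 3.4 already use ≥ for the lower step, so the other edits are to the two thresholds in 5.3.

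Leave secondary endpoint 2.3.2.2 unchanged. It will then differ from the 10 mg trigger at exactly 160 and exactly 110, which does no harm because a treatment trigger need not equal an endpoint cut-off.

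The cost is a minor text amendment with IRB approval and a short reminder to labor and delivery, postpartum and study staff. It adds no visits, procedures or participants.
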